4.2. Scientific Rationale for Study Design

pSS is characterized by mononuclear inflammatory infiltrates and IgG plasma cells in salivary and lacrimal glands that lead to irreversible destruction of the glandular tissue and is accompanied by a sensation of dryness of mouth and eyes. B cells play a central role in the immunopathogenesis and exhibit signs of hyperactivity.¹

In addition, autoantibodies can create immune complexes that maintain and amplify the production of IFN alpha. This combination results in a cycle of immune activation that leads to tissue damage. Currently, no immunomodulatory treatment is available for pSS. In this study, we aim to evaluate the effect of efgartigimod, an FcRn antagonist that can rapidly reduce IgG, including pathogenic antibodies. Efgartigimod contributes to successfully treat pSS and has the potential to improve disease manifestations by the reduction of IgG autoantibodies and immune complexes in pSS.

In the present OLE study (ARGX-113-2211), the long-term safety, efficacy, PD, and PK of efgartigimod will be evaluated in participants with pSS.

The study includes a 48-week treatment period in which patients will receive QW or Q2W doses of efgartigimod 10 mg/kg by IV infusion, ie, at the same dose per body weight, and mode of administration as in the preceding qualifying parent studies.

The treatment allocation (efgartigimod or placebo) from the qualifying studies will be kept blinded in current study.

The primary outcome measure is the ongoing safety of efgartigimod for approximately 1 year after completing the qualifying study. The endpoint aims to demonstrate that efgartigimod is a safe long-term treatment option for pSS. The safety endpoints selected for this study are those considered to be standard for any clinical trial evaluating the safety of an IMP.

The secondary endpoint is the effect of efgartigimod compared to placebo on CRESS (Section 8.2.1). The CRESS composite measures systemic disease activity, patient-reported symptoms, tear gland function, salivary gland function, and serology, developed to assess treatment efficacy in participants with pSS.

All other secondary efficacy endpoints complement the first secondary endpoint and provide additional information on efficacy (ESSDAI, clinESSDAI, ESSPRI, STAR [Section 8.2]), histology, PK, PD, and immunogenicity. The totality of data from all endpoints used in the study will be utilized to determine treatment response in this population.

4.3. Justification for Dose

Doses of efgartigimod 10 mg/kg either QW or Q2W will be administered. For responders a Q2W regimen has been selected to evaluate whether a less frequent dosing regimen can maintain clinical efficacy, while the QW regimen for nonresponders targets efgartigimod's to achieve a near maximal total IgG reduction (PD effect), thereby maximizing the chance of a clinical response on the efficacy outcomes in nonresponders.

As the hypothesis for treating pSS with efgartigimod is to reduce the pathogenic autoreactive IgG, the selected doses and dose regimen target a nearly maximal PD effect (ie, reduction of pathogenic IgGs). The chronic nature of pSS reflects the need for chronic treatment to maintain pathogenic IgG autoantibody suppression and symptom reduction.

The cumulative data from a phase 1 study in healthy adult subjects; phase 2 studies in participants with gMG, ITP, and pemphigus; phase 3 studies in gMG; and PK/PD modeling results demonstrate that a 10 mg/kg efgartigimod dose administered QW through IV infusion achieved 60% to 70% total IgG reduction, including the reduction of pathogenic autoantibodies. Maximal IgG reduction was associated with clinical efficacy observed in gMG, ITP, and pemphigus studies. Furthermore, this dose has been safe and well-tolerated in all study populations and has demonstrated similar PK and PD profiles across indications. Accordingly, the 10 mg/kg IV dose regimen (QW or Q2W) was selected for this study.

4.4. End-of-Study Definition

The end-of-study is defined as the date of the last participant's last visit.

A participant will have completed the study if the SFV assessments have been completed.

5. STUDY POPULATION

Prospective approvals of protocol deviations to enrollment criteria, also known as protocol waivers or exemptions, are not permitted.

5.1. Inclusion Criteria

Participants can be included in the study only if all of the following criteria apply:

1. Is at least the legal age of consent for clinical trials when signing the ICF
2. Is capable of providing signed informed consent, as described in Section 10.1.3, and complying with protocol requirements
3. Agrees to use contraceptive measures consistent with local regulations and the following:
 - a. WOCBP (defined in Section 10.4.1) must have a negative urine pregnancy test at baseline before receiving IMP (Section 10.4.2.1)
4. Has completed the qualifying efgartigimod pSS studies and agrees to continue study drug treatment without interruption in the extension study

5.2. Exclusion Criteria

Participants will be excluded from the study if any of the following criteria apply:

1. Clinically significant disease (including newly diagnosed malignancy or cardiovascular disease) or intention to have surgery during the study; or any other medical condition that, in the investigator's opinion, would confound the results of the study or put the participant at undue risk
2. Pregnant or intention to become pregnant during the study
3. Any severe systemic pSS manifestation that may put the participant at undue risk based on the investigator's opinion

5.3. Lifestyle Considerations

Not applicable.

5.4. Screen Failures

Eligibility to roll over must be verified at the last visit of the preceding qualifying studies.

Participants who consent to participate in the clinical trial but fail to meet the inclusion and exclusion criteria before IMP administration will be considered screen failures and will be captured as "enrollment failures".

Individuals who do not meet the criteria for participation in this study (screen failures), based on the results from assessments in the preceding study, may not be rescreened.

5.5. Criteria for Temporarily Delaying Enrollment

Not applicable.

6. STUDY INTERVENTION(S) AND CONCOMITANT THERAPY

Efgartigimod is the IMP in this OLE study and is manufactured according to Good Manufacturing Practice regulations.

6.1. Investigational Medicinal Product Administered

Table 3: IMP Administered

Intervention label	Efgartigimod IV
Intervention name	Efgartigimod IV
Intervention description	Sterile, colorless, clear concentrate solution for IV infusion. Efgartigimod 20 mg/mL, administered IV
Type	Biologic
Dose formulation	Infusion
Unit dose strength(s)	10 mg/kg QW or Q2W ^a
Route of administration	IV infusion
Use	Experimental
IMP and NIMP/AxMP	IMP
Sourcing	Centrally by the sponsor/designee
Packaging and labeling	IMP will be provided in glass vials. Each vial will be labeled per country requirements
Former name	ARGX-113

AxMP = auxiliary medicinal product; IMP = investigational medicinal product; IV = intravenous;
NIMP = noninvestigational medicinal product; Q2W = every 2 weeks; QW = once weekly

^a QW or Q2W frequency dependent on responder status

6.2. Preparation, Handling, Storage, and Accountability

- The IMP will be supplied to the investigational site by the sponsors' designated IMP supply vendor.
- The pharmacy manual provides detailed instructions on the preparation, handling, storage, accountability, and disposition of unused IMP.
- The investigator or designee is responsible for the correct and safe storage of the IMP. All IMP must be stored in a secure, environmentally controlled, and monitored (manual or automated) area following the labeled storage conditions, with access limited to the investigator and authorized site staff.
- The investigator or designee must confirm that appropriate temperature conditions have been maintained for all IMP received during transit. Any discrepancies are reported and resolved before using the IMP.

- Only participants enrolled in the study are permitted to receive IMP, and only authorized site staff or designee are allowed to supply IMP.
- Appropriate dilutions in a 0.9% saline solution in an infusion bag will be prepared before administration with an IV pump.
- IMP must be stored refrigerated (2°C to 8°C) and protected from direct sunlight in secondary packaging. Do not shake IMP or expose it to freezing temperatures.
- Participants will be observed for at least 30 minutes after the end of IMP infusion for routine safety monitoring.
- The pharmacy manual and home guide provide further guidance and information for the final disposition of unused IMP.
- Accountability of home-administered IMP will be documented as instructed in the home guide.

6.3. Assignment to IMP

All participants will receive efgartigimod 10 mg/kg by IV infusion either Q2W or QW based on whether the participant is a responder or nonresponder, respectively.

6.4. Blinding

ARGX-113-2211 is an open-label study. The treatment allocation (efgartigimod or placebo) from the double-blind qualifying studies will be kept blinded in the current study.

6.5. Study Compliance

IMP infusions must occur at the site for a minimum of 3 consecutive visits (for QW dosing regimen: baseline visit and the week 1 and 2 visits; for Q2W dosing regimen: baseline visit and the week 2 and 4 visits) before home infusions are allowed. If doses are missed at 1 or more of these visits, then dosing at subsequent visits will also be on-site. IMP administration at home will not commence until after 3 doses have been administered on-site.

IMP may be administered at home (by a health care professional [nurse]) for other visits. Participant compliance with IMP administration at home will be assessed by direct questioning during the site visit and documented in the source documents and relevant forms. The date and time of each dose administered will be recorded as well as the total dose administered at each visit. Deviation(s) from the prescribed dosage regimen will be recorded.

6.6. Dose Modification

The maximum total efgartigimod dose per efgartigimod infusion is 1200 mg for participants weighing ≥ 120 kg. The IMP weight-based dose will be recalculated if a participant's weight has changed (increased or decreased) by more than 10% from OLE baseline (ie, weight prior to IMP infusion on day 1 of the ARGX-113-2211 study).

Modifications to the schedule of dosing are permitted as described in Section 4.1.

6.7. Continued Access to IMP After the End of the Study

At the end of the study, argenx cannot guarantee continued access for participants but will comply with all local laws and regulations.

6.8. Treatment of Overdose

Any dose of efgartigimod greater than the intended QW or Q2W amount will be considered an overdose.

The sponsor does not recommend specific treatment for an overdose.

In the event of an overdose, the investigator or treating physician will:

- Evaluate the participant to determine if IMP will be interrupted
- Closely monitor the participant for any AE/SAE and laboratory abnormalities (as medically appropriate and at least until the next scheduled follow-up)
- Record the overdose in the eCRF and the quantity of the excess dose as well as the duration of the overdose

6.9. Prior and Concomitant Therapy

Participants must maintain a stable regimen of medications throughout the study. Any medication (including over-the-counter or prescription medicines, recreational drugs, vitamins, and/or herbal supplements [including Chinese traditional medicine]) or other specific categories of interest that the participant is receiving at the time of enrollment or receives during the study must be recorded and include the following information:

- Reason for use
- Dates of administration, including start and end dates
- Dosage information (ie, dose and frequency)

The following medications or treatments are not permitted during the periods listed in [Table 4](#).

Table 4: Prior and Concomitant Therapy

Medication	Period participant is receiving IMP	Follow-up period
Live or live-attenuated vaccines	Prohibited	Permitted from 28 days after the last IMP dose
SCIg	Prohibited	Permitted
IVIg	Prohibited	Permitted
Corticosteroid steroids:		
Intra-muscular or intravenous corticosteroids	Prohibited	Permitted
Oral corticosteroids	Stable dose up to 10 mg daily	Permitted

Medication	Period participant is receiving IMP	Follow-up period
Inhaled corticosteroids	Permitted	Permitted
Intra-articular steroids	Prohibited	Permitted
Topical steroids	Topical (non-ophthalmic) steroids are permitted Topical ophthalmic steroids are prohibited.	Permitted
DMARDs		
Conventional DMARDs / Antimalarials	Permitted HCQ, CQ, AZA, MTX, MMF, leflunomide or cyclosporin at stable dose	Permitted
Cyclophosphamide	Prohibited	Permitted
Biologic DMARDs	Prohibited	Permitted
Targeted synthetic DMARDs:		
JAK inhibitors	Prohibited	Permitted
IMPs:		
IMP in another clinical trial	Prohibited	Permitted
Nonbiologic IMP in another clinical trial	Prohibited	Prohibited
Biologic IMP in another clinical trial	Prohibited	Prohibited
Other:		
Chinese traditional medicine with known immunomodulatory action	Prohibited	Permitted
Anticholinergic agents	Permitted at stable dose	Permitted
Topical symptomatic medications for pSS	At visits with planned efficacy assessments, participants will be required to withhold ophthalmic lubricants, ophthalmic lubricating ointments, hydroxyl cellulose ophthalmic inserts, and saliva substitutes before efficacy assessments are completed.	Permitted
Pharmacological topical ophthalmic agents (eg, NSAIDs, cyclosporine)	Prohibited	Permitted

Medication	Period participant is receiving IMP	Follow-up period
Pilocarpine and/or any other pharmacological stimulant for salivary and lacrimal glands	Permitted at stable dose Not to be taken within 24 hours of clinical assessments	Permitted

AZA = azathioprine; CQ = chloroquine; DMARD = disease-modifying antirheumatic drug; EDV = early discontinuation visit; HCQ = hydroxychloroquine; IMP = investigational medicinal product; IVIg = intravenous immunoglobulin; JAK = Janus kinase; MMF = mycophenolate mofetil; MTX = methotrexate; NSAID = non-steroidal anti-inflammatory drug; pSS = primary Sjögren's syndrome; SCIG = subcutaneous immunoglobulin

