7.1. Discontinuation of IMP

7.1.1. Permanent Discontinuation

Permanent discontinuation of IMP occurs when the participant stops receiving the IMP before the end of the study, does not resume receiving IMP, and does not withdraw informed consent.

The investigator will document the primary reason for early discontinuation of IMP.

Participants who permanently discontinue IMP will complete the EDV.

The study sites will attempt to perform the EDV within 7 days after the participant's final IMP administration. The SFV will occur 56 ± 3 days after the participant's final IMP administration.

Additionally, the following circumstances will result in the permanent discontinuation of IMP:

- The participant becomes pregnant or intends to become pregnant (see Section 8.3.5)
- The investigator considers discontinuing IMP is in the participant's best interest (the sponsor will be informed)
- The participant develops an SAE or AE that contraindicates further administration of IMP in the investigator's opinion or an AE of CTCAE severity grade 4 that is considered related to IMP by the sponsor
- The participant develops a new or recurrent malignancy except for basal cell carcinoma of the skin, regardless of relationship to IMP
- The participant receives a prohibited medication or substance (Section 6.9)

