5.1. Full Analysis Set [FAS]

The full analysis set (FAS) will contain all enrolled subjects in the OLE study.

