13. EFFICACY OUTCOMES

13.1. Efficacy Endpoints

The efficacy analyses will be performed for the FAS and will be analyzed on data observed.

Copyright © 2009, 2010, 2012, 2016, 2018, 2019, 2021, 2024 IQVIA. All rights reserved. The contents of this document are confidential and proprietary to IQVIA Holdings Inc. and its subsidiaries. Unauthorized use, disclosure or reproduction is strictly prohibited.

13.1.1. Proportion of CRESS Responders on ≥ 3 of 5 items at Week 24 and 48

The CRESS composite measures below mentioned assessments which are developed to assess treatment efficacy in participants with pSS:

- 1) Systemic disease activity: clinESSDAI
- 2) Patient-reported symptoms: ESSPRI
- 3) Tear gland function: Schirmer’s test and OSS.
- 4) Salivary gland function: UWSF rate and SGUS
- 5) Serology (serum IgG and/or RF)

The efficacy endpoint is the proportion of responders on ≥ 3 non-missing of 5 items at week 24 and 48 using CRESS.

CRESS consists of the following items, with definitions of treatment response and lower disease activity:

1) Systemic disease activity: This will be measured with clinESSDAI (Seror [a], et al., 2016)⁸.

The clinESSDAI consists of 11 domains, related to organ involvement (cutaneous, pulmonary, renal, articular, muscular, peripheral nervous system, central nervous system, hematological, glandular, constitutional, and lymphadenopathic). The ClinESSDAI includes all ESSDAI domains except the biological domain.

Table E: Domain Weights of ClinESSDAI

Domain (activity level)	ClinESSDAI Weights
Constitutional (0-2)	4
Lymphadenopathy (0-3)	4
Glandular (0-2)	2
Articular (0-3)	3
Cutaneous (0-3)	3
Pulmonary (0-3)	6
Renal (0-3)	6
Muscular (0-3)	7
Peripheral nervous system (0-3)	5
Central nervous system (0-3) ^{Seror 2015}	5
Hematological (0-3)	2
Biological (0-2)	NA*

Copyright © 2009, 2010, 2012, 2016, 2018, 2019, 2021, 2024 IQVIA. All rights reserved. The contents of this document are confidential and proprietary to IQVIA Holdings Inc. and its subsidiaries. Unauthorized use, disclosure or reproduction is strictly prohibited.

Domain (activity level)	ClinESSDAI Weights
Score total	0-135

*NA: Not Applicable

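### Starting or raising a stable-dose-only background therapy has no clear consequence in the protocol and no visible rule in the SAP, so later improvement is counted as response

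*Protocol*

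**What the plan says.** Protocol 6.9 sets a general rule: "Participants must maintain a stable regimen of medications throughout the study". Dose, frequency, dates and reason for use must be recorded for every medication. Table 4 is introduced with "The following medications or treatments are not permitted during the periods listed in", yet its entries are a mixture of prohibited, permitted and conditionally permitted. For the period on IMP, the conditional rows that matter here are:

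- oral corticosteroids: "Stable dose up to 10 mg daily"
- conventional DMARDs and antimalarials: "Permitted HCQ, CQ, AZA, MTX, MMF, leflunomide or cyclosporin at stable dose"
- pilocarpine and other salivary or lacrimal stimulants: permitted at a stable dose, and "Not to be taken within 24 hours of clinical assessments"

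Among the events that end IMP permanently, Protocol 7.1.1 lists: "The participant receives a prohibited medication or substance (Section 6.9".

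SAP 13.1 says of efficacy: "The efficacy analyses will be performed for the FAS and will be analyzed on data observed". SAP 5.1 adds: "The full analysis set (FAS) will contain all enrolled subjects in the OLE study". No per-protocol set is defined, and both documents state that no estimands have been defined. SAP 8.2 counts and lists protocol deviations, and SAP 10 tabulates and lists concomitant therapies. Neither links them to response.

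**The concern.** A participant who starts methotrexate, or begins an oral corticosteroid within the Table 4 ceiling, and then improves can meet the clinESSDAI, ESSDAI, ESSPRI, CRESS or STAR response definition at week 24 or 48. Nothing visible in SAP 13.1 treats that participant differently from one who improved on efgartigimod with unchanged background therapy. In a randomised study a control arm would show how much improvement goes with added therapy. This study has one open-label arm, so the reported proportion mixes the two and a reader cannot see by how much.

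The clinESSDAI score also sets QW or Q2W dosing under Protocol 4.1, so the regimen subgroups in SAP 13.1.5 would inherit the same ambiguity.

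**Working it through.** **Step 1. Does 7.1.1 cover the event?** Table 4 entries for the period on IMP:

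| Entry | Rows (examples) | Covered by 7.1.1? |
|---|---|---|
| Prohibited | cyclophosphamide, biologic DMARDs, JAK inhibitors, intramuscular/intravenous and intra-articular steroids | Yes |
| Stable dose only | oral corticosteroids, conventional DMARDs/antimalarials, secretion stimulants | Not stated for a new start or an increase |

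The Table 4 lead-in and the stable-regimen sentence support reading a breach as not permitted, and so within 7.1.1. The row labels, and 7.1.1's use of the word prohibited, support the opposite reading. An oral corticosteroid dose above the ceiling is more easily read as not permitted. The gap is clearest for a start or change within it.

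**Step 2. What happens to the score if IMP continues?** SAP 7.1 sends missing-data handling to the endpoint sections. Sections 13.1.1 to 13.1.6 define the scores and responses but contain no rule for a therapy change. With all enrolled participants in the FAS and observed data analysed, the post-change value is used.

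**Step 3. Which endpoints can be affected?** Systemic therapy could affect any of them. A secretion stimulant bears on three items: ESSPRI (through dryness), tear-gland function and salivary-gland function.

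- CRESS needs at least 3 of 5 items, and these are 3 items.
- STAR needs at least 5 points, and these are worth 3 + 1 + 1 = 5.

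They can therefore reach either threshold on their own. No ESSDAI or clinESSDAI domain measures tear or salivary flow. The 24-hour withholding rule limits a stimulant's effect on the flow tests. It does less for ESSPRI, whose recall period in SAP 13.1.1 is two weeks.

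**Step 4. Size.** The plan gives no expected response rate and no frequency of therapy changes, so there is no figure to reproduce. The following is for scale only.

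Inputs: n = 30 (Protocol 9.5, an approximate maximum); exact two-sided 90% CI (SAP 13.1.1); observed responders x and affected responders k are assumed.

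Formulas: observed proportion = x/n; after reclassification = (x − k)/n; difference = k/n. Clopper-Pearson limits for y responders are Beta(0.05; y, n − y + 1) and Beta(0.95; y + 1, n − y).

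| Observed | k | Reclassified |
|---|---|---|
| 15/30 = 50.0% (33.9–66.1) | 1 | 14/30 = 46.7% (30.8–63.0) |
| 15/30 = 50.0% (33.9–66.1) | 3 | 12/30 = 40.0% (25.0–56.6) |
| 15/30 = 50.0% (33.9–66.1) | 5 | 10/30 = 33.3% (19.3–49.9) |
| 9/30 = 30.0% (16.6–46.5) | 3 | 6/30 = 20.0% (9.1–35.7) |
| 21/30 = 70.0% (53.5–83.4) | 3 | 18/30 = 60.0% (43.4–75.0) |

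Each affected responder is worth 1/30 = 3.3 points. SAP 7.2 leaves missing values out of denominators, so the step grows as data are lost: 1/24 = 4.2 points and 1/20 = 5.0 points. SAP 7.2 also asks for summaries by parent-study treatment. If rollover follows the parent study's 2:1 ratio (an assumption, giving 20 and 10), one responder is worth 5.0 or 10.0 points.

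**The case against.** The case for leaving the plan alone has weight. Reporting what was observed, whatever the background therapy, is a legitimate choice for an extension study. Here no hypothesis is tested, results are not used inferentially, and the primary endpoint is safety. Deviations and concomitant therapies are listed, so affected participants can be found afterwards. SAP 13.2 and 13.3 are redacted, and SAP Appendix 3 and the deviation management plan are not available, so a supplementary analysis elsewhere cannot be excluded. An escalating participant who still fails to respond changes nothing. The illustrated intervals overlap heavily.

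Most of this stands. It limits the weight of the point and argues for keeping the observed-data result. It does not supply a visible rule for the secondary endpoints, and a listing does not tell a reader what the response rate would be without those participants.

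A reader might also infer that nonresponders facing the week 24 therapeutic-failure evaluation would be given extra therapy to keep them on IMP. The documents do not support treating that as expected: it would breach 6.9, and Protocol 4.1 lets the PI keep a week 24 nonresponder on QW dosing.

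**Conclusion.** The gap holds in a limited form. It is unclear whether starting or increasing a stable-dose-only therapy counts as receiving a prohibited medication. If the participant stays on IMP, the visible SAP rule counts later improvement as response. The effect is 3.3 points per affected observed responder when 30 are analysed, and more with fewer. How many will be affected is unknown.

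Three stronger readings go too far:

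- That such a breach certainly has no consequence. The text allows either reading, and 7.1.1 also lets the investigator stop IMP in the participant's interest.
- That the response rates are biased upward by a known amount. That needs participants who escalate, improve because of it, and would otherwise not have responded; the documents give no count of these.
- That the gap extends to all DMARDs. Cyclophosphamide, biologic DMARDs and JAK inhibitors are labelled prohibited and fall under 7.1.1.

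**What to change.** In SAP 13.1, keep the observed-data result and show beside it a second analysis of the week 24 and 48 responder endpoints, with these rules:

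- A participant who, after OLE baseline and before the assessment, started or increased an oral corticosteroid or a conventional DMARD/antimalarial for pSS counts as a nonresponder. The recorded reason for use decides whether it was for pSS, so treatment of an unrelated condition does not force nonresponse.
- A start or increase of a secretion stimulant counts as nonresponse only on the ESSPRI, tear-gland and salivary-gland items and their contribution to CRESS and STAR. ESSDAI and clinESSDAI endpoints are left as observed.
- Change from baseline is shown with and without values after the escalation.

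The cost is one further derivation from data that 6.9 already requires, and supplementary response rates that may be lower. One consequence should be stated in the SAP. With the three stimulant-related items set to nonresponse, at most 2 CRESS items and 3 + 1 = 4 STAR points remain, so that participant cannot be a CRESS or STAR responder in this analysis. This is a reason to present it beside the observed result and not in its place.

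Separately, Protocol 6.9, Table 4 and 7.1.1 must be reconciled on whether breaching a stable-dose row is receipt of a prohibited medication. Which clinical rule applies is for the sponsor to decide.
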